9.2 Potential Benefits to the Subject

It is possible that a study subject will not receive any benefits from treatment with the Coil.

Potential benefits of the Coil treatment that may be realized by study subjects include overall reduction in number or severity of symptoms related to emphysema and improved quality of life.

Another potential benefit to subjects participating in the study is the ability to learn more about their emphysema based on the assessments that will be performed throughout the course of the study.

For subjects with Medicare, Medicaid and/or third party insurance (private insurance) required to comply with the US Medicare Clinical Trial Policy rules for clinical trial coverage, many of the tests and procedures necessary for study completion will be billed to them. Tests and services required by the study that are not covered by the Medicare Clinical Trial Policy rules will be paid by PneumRx, Inc., the study sponsor.

The results of this study may help other emphysema subjects to gain access to a device that may improve their quality of life and general health.

10 Study Monitoring

PneumRx and its designee(s) for Data Management and Biostatistics will be responsible for coordinating and conducting the handling of clinical study data.

Before acceptance of the clinical data, PneumRx and its assigned Clinical Monitor designee(s) will review the data entered on eCRFs for completeness and adherence to the protocol based upon source documentation verification (SDV). Procedures to be followed and the data to be fully monitored to SDV will be described in detail in the Monitoring Plan.

PneumRx and its designee(s) will meet with the investigator to ensure that subjects will be properly selected and enrolled, that the methods described in the study protocol are thoroughly understood and that the method(s) surrounding clinical data collection and capture are understood.

Assigned Clinical Monitors of PneumRx will visit the clinical site(s) periodically during the course of the study to perform SDV and perform device reconciliation. The Investigator and Institution must guarantee direct access to associated medical records by designated monitors and appropriate regulatory authorities.

The study may be subject to a quality assurance audit by either PneumRx or by appropriate regulatory authorities. It is important that the Investigator and the assigned authorized study personnel are available during monitoring visits and possible audits and that sufficient time is dedicated to the process.

11 Responsibilities of the Sponsor

The sponsor of this clinical trial is PneumRx, Inc. of Mountain View, CA, U.S.A. The sponsor is committed to:

- Conducting this clinical trial in compliance with Good Clinical Practice (GCP) Guidelines as required by United States Food and Drug Administration Code of Federal Regulations and the Declaration of Helsinki (2008), as well as with any local laws, regulations or requirements applicable to any particular study site.

- Protecting the rights, health, safety and welfare of study subjects; the sponsor is responsible for obtaining and reviewing copies of IRB/Research Ethics Board approvals and will verify that appropriate subject Informed Consent is obtained.
- Informing the clinical investigator of any new information about the study that may affect the health, safety or welfare of the subjects, or which may influence their decision to continue participating in the study.
- Providing the clinical investigator with the study protocol and the eCRFs on which to document the study evaluation variables for each subject entered into the Study.
- Providing the data collection and management, statistical analysis and study report-writing resources necessary to complete reporting of the study results.
- Ensuring proper investigative site training and monitoring.
- Selecting qualified investigators with adequate facilities to conduct this clinical trial and establishing written Investigator's Agreements.
- Maintaining copies of correspondence, records of shipment and disposition of devices, adverse device effects, records related to the signed investigator agreements, and other records related to the clinical study.
- Securing and maintaining US FDA IDE approval prior to treatment of any subjects.
- Provision of SAE reports to FDA as required per DMC determination of reportability and support of investigators as needed.

12 Responsibilities of the Principal Investigator

The Principal Investigator (PI) participating in this clinical trial must hold a current medical license as a physician in his/her country of employment for the full duration of the study. The PI will affirm by his/her signature on the Investigator Agreement that he/she will fulfill his/her responsibilities relative to this clinical trial.

- **Subject Selection**

The investigator is responsible for ensuring that all subjects entering the study conform to the subject inclusion criteria and that no exclusion criteria apply.

- **IRB/EC Approval**

The investigator is responsible for obtaining IRB/EC approval from the institution at which he or she shall perform the procedure, prior to consenting or enrolling any subjects in the study. The Informed Consent document to be used will also be submitted by the Investigator to the IRB/EC for approval prior to initiation of the study. The investigator is also responsible for providing any other additional documentation relevant to the study as

required by IRB/EC for complete review of the study. Written assurance of IRB/EC approval of the trial plan and the Informed Consent document must be provided to the sponsor prior to initiation of the study.

- **Informed Consent**

The investigator is responsible for fully discussing the nature of the study, the possible risks, and the alternative treatments (including lung volume reduction surgery) with prospective subjects prior to their enrollment in the study. The investigator is responsible for obtaining written Informed Consent from each subject prior to enrollment in the trial. The ICF to be used should be the version of the document approved by the IRB/EC. The signed ICF will be maintained in the subject's medical record, and a copy of the signed ICF will become an integral part of each case report file retained by the Investigator. A copy of the signed ICF shall also be given to the subject who signed the form.

The approved ICF specific to each responsible IRB/EC will be used by the Investigator for this study.

- **Subject Evaluations and Data Reporting**

The investigator's designee is responsible for performing the subject evaluations as described in this trial plan. Regulations require that the study investigator maintain information in the study subject's medical records (i.e. source documentation) to corroborate data collected on the eCRFs.

All information generated by the subject evaluations is to be transferred from the source documentation and recorded using EDC. Paper source documents should be completed in blue or black ink or should be typewritten. Any necessary corrections should be made by a single strikethrough in ink, initialed and dated by study site personnel. Correction fluid may not be used. The investigator will review, correct as needed, and sign off on the accuracy and completeness of the data entered on the eCRFs. Subject casebooks may be printed for review by authorized regulatory bodies. Original laboratory reports are to be retained by the Investigator, and the resulting data shall be entered onto the appropriate eCRFs.

The sponsor will routinely monitor the subject data on an ongoing basis to support data quality and integrity. Source records will be reviewed as necessary to support assessment of data collected and reported using study eCRFs.

The investigator is also responsible for submitting reports to PneumRx, Inc. and the reviewing IRB/EC as specified in this protocol.

- **Protocol Deviations**

The study investigator should not deviate from this protocol unless the trial plan poses unacceptable risks to the health or welfare of the involved individual subject.

The investigator shall notify PneumRx Inc. and the reviewing IRB/EC of any deviation from the protocol intended to protect the life or physical well-being

of a subject in an emergency. Such notice shall be given as soon as possible, but in no event later than five working days after the emergency occurred. Except in such an emergency, prior approval of PneumRx Inc. is required for any deviation from the protocol. Approval from the IRB/EC also is required if these changes or deviations are expected to affect the rights, safety or welfare of human subjects.

- **Record Retention**

The investigator shall maintain all original records as required by local regulation or law and at a minimum shall maintain documents until after FDA has approved the RePneu Coil System.

- **Investigational Device Accountability**

The investigator must maintain accurate records of the receipt of all investigational devices shipped by the sponsor, including the date and lot numbers of devices received. In addition, accurate records must be kept regarding the date and quantities of investigational devices received, dispensed and returned. Information regarding the specific identification numbers for investigation devices used is to be recorded onto the appropriate device accountability log for each subject undergoing the treatment procedure throughout the course of the study. The investigator must assure that study supplies are dispensed only to subjects properly enrolled in the study and under the direct supervision of the investigator or co-investigators.

All used and unused investigational supplies, as well as all labeled containers, are to be returned to the sponsor as soon as practical upon request by the sponsor or designee or upon completion of the study. Investigational material accounting procedures must be completed before the study is considered terminated.

13 Good Clinical Practice & Regulatory Requirements

Informed Consent

Written Informed Consent for the study must be obtained from all subjects who will participate in this clinical trial prior to their participation.

Individual institutions may revise the sponsor-provided ICF with information that would meaningfully add to the protection of the rights and welfare of subjects. Prior to submitting the revised ICF to the IRB/EC for review, the investigator is to receive authorization of the revisions by PneumRx Inc. Clinical Affairs staff. The IRB/EC at each clinical site will then review and approve the ICF prior to study initiation. The investigator at each institution shall submit the approved ICF to the sponsor who shall review it to ensure compliance with applicable regulations.

IRB/EC Approval

This Study may not be initiated at any site until the IRB/EC has reviewed and approved the study protocol and the Informed Consent documents. Written committee approval is required prior to study initiation. The sponsor will review all documents and notify the site when screening and enrollment may begin.

Subject Confidentiality

1. SYNOPSIS OF STUDY DESIGN AND PROCEDURES

The purpose of the statistical analysis plan (SAP) is to provide a detailed and comprehensive description of the planned methodology and analysis for Protocol CLN0016.p. D, the CROSSOVER Study. This plan is based on the version CLN0016.p. D, study protocol dated August 24th, 2015.

1.1 Study Objective

The primary objective of this study is to obtain safety and effectiveness data on patients who were enrolled as Control patients in and completed the Lung Volume Reduction Coil Treatment in Patients with Emphysema (RENEW) study (CLN0009).

1.2 Study Design

This will be a prospective, multicenter, open label, single-arm study.

1.2.1 Effectiveness Endpoints

- 6MWT: absolute change from baseline at 12 months in the 6 Minute Walk Test
- 6MWT: responder analysis, comparing baseline to 12 months, responders defined as those with an improvement of ≥ 25 meters^[1]
- Forced Expiratory Volume in one second (FEV₁): percent change in FEV₁ results measured using spirometry, comparing baseline to 12 months
- Saint George's Respiratory Questionnaire (SGRQ): absolute difference in SGRQ total score comparing baseline to 12 months.
- SGRQ: responder analysis, comparing baseline to 12 months, responders defined as those with an improvement of ≥ 4 points^[2]
- SGRQ: absolute difference in individual domain scores comparing baseline to 12 months
- FEV1: responder analysis, comparing baseline to 12 months, responders defined as those with an improvement of $\geq 10\%$.
- Residual Volume (RV): absolute difference in RV measured using plethysmography, comparing baseline to 12 months^[3-5]
- RV: responder analysis, comparing baseline to 12 months, responders defined as those with an improvement (decrease) of .35L
- Vital Capacity (VC): absolute difference in VC measured using plethysmography, comparing baseline to 12 months
- Residual Volume/Total Lung Capacity (RV/TLC): absolute difference in RV/TLC measured using plethysmography, comparing baseline to 12 months^[6-8]

1.2.2 Safety Endpoints

The primary safety analysis will tabulate subjects who experience one or more major complication(s) within 12 months post-baseline (and within defined blocks of time post-baseline). Major complications will be determined/adjudicated by the Clinical Events Committee.

Major Complications:

- Death;
- Pneumothorax that requires a chest drainage tube for more than 7 days (from time of chest drainage tube insertion to the time of chest drainage tube removal);
- Hemoptysis requiring blood transfusion(s), arterial embolization, or surgical/endoscopic procedure;
- COPD exacerbation that becomes life-threatening or disabling as a result of an increase in respiratory symptoms requiring in-patient hospitalization of >7 days with or without mechanical ventilation;
- Lower Respiratory Infections (including pneumonia) defined by new or increased clinical symptoms such as fever, chills, productive cough, chest pain, dyspnea and an infiltrate on plain chest x-ray and hospitalization for administration of intravenous antibiotics and/or steroids;
- Respiratory failure defined as a requirement for mechanical ventilatory support (whether via endotracheal tube or mask) for >24 hours; and
- An unanticipated bronchoscopy in order to remove one or more Coils due to a device-related AE. (Note: This definition does not include re-positioning, replacement or removal of the Coil(s) during the initial placement procedure.)

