4.5 Safety Evaluation

Safety will be evaluated by collection of AEs and SAEs from entry into the study (Visit 1) until Visit 10 (12 months Follow-up from Visit 2) or until the subject has completed or terminated from the study.

Prior to discharge after treatments and at each phone call or follow-up visit, subjects will be instructed to report to the investigator any adverse physical or mental changes they experienced since the previous visit/interview. All such AEs/SAEs reported by the subjects or observed by the investigators will be recorded.

Safety data from the various OUS studies that PneumRx has conducted to date have been collected and analyzed. A summary of the safety data is provided in Section 2.4, above.

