1.3 Analysis Populations

1.3.1 Intent-to-Treat Population

The Intent-to-Treat (ITT) population will include patients who enrolled in the CROSSOVER study, regardless of whether or not treatment was attempted.

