1.4 Sample Size and Power Calculation

The CROSSOVER Study was designed to provide an opportunity for qualifying Control subjects from the RENEW study to receive the LVRC treatment once their participation in the randomized phase of the RENEW study was complete; all qualifying subjects who wished to participate and met the enrollment criteria were enrolled. Thus, the study sample size was not based on a primary and null hypothesis, or power calculation and results will only be presented descriptively.

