2. ANALYSIS CONSIDERATIONS

2.1 Subject Disposition

The number of subjects screened, enrolled and treated in the study will be presented. Additionally, the number and percentage of subjects who complete the study to 12 months, 24 months, 36 months, 48 months and 60 months, and who terminate the study prematurely (by visit), will be presented including reasons for premature termination.

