2.3.2.3 Adverse Events

MedDRA system organ classes and preferred terms will be summarized for all AEs. Summaries will include event and subject counts. For the events summarized by subject counts, each subject will be counted only once within a system organ class or a preferred term by using the adverse events with the highest severity within each category.

SAE, AEs, and AEs related to device or procedure will be summarized separately. Additionally, summaries for major complications will also be included. A high level summary for SAEs and AEs will also be provided. All summaries will be presented by each follow up time period. Similarly, device or procedure related SAEs and non-SAEs will be presented by severity.

In addition, all information pertaining to AEs noted during the study will also be listed by subject. Details of the line listing by subject will include verbatim term given by the Investigator, preferred term, system organ class, start date, stop date, severity, and device or procedure relatedness. The AE onset will also be shown relative (in number of days) to the day of the procedure.

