E. Date imputations are applied to the process of assigning treatment period and study day and should be retained in the derived database, but the data listings should display the original, partially missing dates.

F. Specifications regarding the inclusion of AE/CM/PD records

- 1) up to 12-month visit are defined as follows:
 - Completed 12 month visit – then include all records with AE/CM/PD onset dates \leq the actual 12 month visit date.
 - Missing 12 month visit – then include all records with AE/CM/PD onset dates \leq 13 months post treatment #1 date.
- 2) 12 – 24 month are defined as follows:
 - Completed 24 month visit – then include all records with AE/CM/PD onset dates \leq the actual 24 month visit date and \geq actual 12 month visit date.
 - Missing 24 month visit – then include all records with AE/CM/PD onset dates \leq 25 months post treatment #1 date and \geq actual 12 month visit date.
- 3) 24 – 36 month are defined as follows:
 - Completed 36 month visit – then include all records with AE/CM/PD onset dates \leq the actual 36 month visit date and \geq actual 24 month visit date.
 - Missing 36 month visit – then include all records with AE/CM/PD onset dates \leq 37 months post treatment #1 date and \geq actual 24 month visit date.
- 4) 36 – 48 month are defined as follows:
 - Completed 48 month visit – then include all records with AE/CM/PD onset dates \leq the actual 48 month visit date and \geq actual 36 month visit date.
 - Missing 48 month visit – then include all records with AE/CM/PD onset dates \leq 49 months post treatment #1 date and \geq actual 36 month visit date.
- 5) 48 – 60 month are defined as follows:
 - Completed 60 month visit – then include all records with AE/CM/PD onset dates \leq the actual 60 month visit date and \geq actual 48 month visit date.
 - Missing 60 month visit – then include all records with AE/CM/PD onset dates \leq 61 months post treatment #1 date and \geq actual 48 month visit date.

G. Unless otherwise noted, the mean (standard deviation) of a set of values should be printed out to one (two) more decimal(s) than the raw value.

e.g., raw: xx
 mean and standard deviation: xx.x and xx.xx
 range (minimum and maximum): xx, xx

- H. All table percentages should be reported with one decimal point unless otherwise noted.

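### The primary safety tabulation makes no allowance for follow-up shorter than 12 months; on the only population the SAP defines, it understates the major-complication risk

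*SAP*

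**What the plan says.** SAP 1.2.2 makes the primary safety analysis a tabulation: it will "tabulate subjects who experience one or more major complication(s) within 12 months post-baseline", and will do the same within blocks of time. Death is one of the listed complications. SAP 2.3.2.3 describes the output for adverse events: "Summaries will include event and subject counts". SAP 2.3.2.1 assigns each event to the block in which it began, but gives no number at risk for any block. Neither document mentions a Kaplan-Meier, cumulative-incidence or person-time estimate.

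SAP 1.3.1 defines one population, ITT, which takes in enrolled patients "regardless of whether or not treatment was attempted". No text assigns this or any other population to the safety tables.

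Incomplete follow-up is foreseen. SAP 2.1 reports the number and percentage of subjects "who terminate the study prematurely (by visit), will be presented including reasons for premature termination". Protocol 4.5 collects events to Visit 10 "or until the subject has completed or terminated from the study". Where the 12-month visit is missing, SAP Appendix 4.1 item F admits records with onset up to "13 months post treatment #1 date". SAP 1.4 adds that "results will only be presented descriptively".

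**The concern.** A subject who leaves at month 3 without a complication has been observed for three months, not twelve. A simple count over all subjects gives that person the same weight as one followed event-free to month 12. A subject who was never treated cannot have a procedure or device complication, but is in the only defined population.

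This matters because the study has a single arm. No concurrent control shares the same loss of follow-up, so the absolute percentage is itself the safety result. Such percentages also get set beside other studies: Protocol Table 5 already compares the device's event rates with those of a sham group from another trial. A rate whose denominator is unwritten cannot be read safely in that way.

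Item F does not settle the matter. It decides which recorded events are counted. For a subject who missed the visit but is still followed, it captures events. For a subject who has withdrawn, no further collection is stated, and the rule says nothing about time at risk.

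**Working it through.** **No figure to reproduce.** The documents state no expected major-complication rate, dropout rate or sample size. All rates below are assumptions, shown as a range.

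**Inputs (assumed).**
- True 12-month risk R: 20%, 30% or 40%.
- Probability w of withdrawing by 12 months if no event occurs first: 5%, 10% or 20%, at a constant rate and unrelated to risk.
- Timing of events: either a constant hazard, or 70% of the cumulative hazard falling in months 0-1 and 2-3. The second pattern mimics the SAP's 0-30-day peri-procedural windows after two procedures about two months apart.

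**Formula, constant hazard.** Put H = -ln(1-R) and W = -ln(1-w).
- Crude proportion over all subjects: C = H/(H+W) × [1 - (1-R)(1-w)].
- Proportion withdrawing event-free: D = W/(H+W) × [1 - (1-R)(1-w)].
- Proportion if event-free withdrawals are dropped from the denominator: C/(1-D).

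**Example, R = 30%, w = 20%.** H = 0.3567, W = 0.2231, H+W = 0.5798, and 1 - 0.70×0.80 = 0.44.
- C = 0.3567/0.5798 × 0.44 = 0.271, a shortfall of 2.9 points.
- D = 0.2231/0.5798 × 0.44 = 0.169.
- C/(1-D) = 0.271/0.831 = 0.326, an excess of 2.6 points.

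**Same example, 70% of the hazard peri-procedural.** The monthly event hazard is 0.3567×0.7/2 = 0.1248 in months 0-1 and 2-3, and 0.3567×0.3/10 = 0.0107 otherwise. The monthly withdrawal rate is 0.2231/12 = 0.0186. Applying the same formula segment by segment gives event proportions of 0.116 (month 0-1), 0.009 (1-2), 0.098 (2-3) and 0.062 (3-12). These sum to 0.285, a shortfall of 1.5 points.

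**Range.** Each cell shows constant hazard / 70% peri-procedural.

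| True risk | Withdrawal | All subjects in denominator | Shortfall (points) | Event-free withdrawals excluded |
|---|---|---|---|---|
| 20% | 5% | 19.5% / 19.8% | 0.5 / 0.2 | 20.4% / 20.6% |
| 20% | 10% | 19.0% / 19.5% | 1.0 / 0.5 | 20.9% / 21.3% |
| 20% | 20% | 18.0% / 19.0% | 2.0 / 1.0 | 22.0% / 22.9% |
| 30% | 5% | 29.3% / 29.6% | 0.7 / 0.4 | 30.6% / 30.8% |
| 30% | 10% | 28.6% / 29.3% | 1.4 / 0.7 | 31.2% / 31.7% |
| 30% | 20% | 27.1% / 28.5% | 2.9 / 1.5 | 32.6% / 33.7% |
| 40% | 5% | 39.1% / 39.5% | 0.9 / 0.5 | 40.7% / 41.0% |
| 40% | 10% | 38.1% / 39.1% | 1.9 / 0.9 | 41.4% / 42.0% |
| 40% | 20% | 36.2% / 38.1% | 3.8 / 1.9 | 43.0% / 44.2% |

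**Never-treated subjects.** This dilution is separate from withdrawal. With 30% risk among the treated and no withdrawal, 5% untreated gives 0.30×0.95 = 28.5%, and 10% untreated gives 0.30×0.90 = 27.0%.

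**The case against.** The strongest reply is that the analysis is descriptive. There is no hypothesis or performance goal, so a shift of a few points changes no decision rule in the documents. Early terminations are reported by visit with reasons, which makes incomplete follow-up visible. The time blocks help too, because the early ones lose few subjects. All of this stands and limits the consequence. It does not remove the need for a defined denominator, and a separate disposition table does not correct the rate.

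A reader might go further and infer that the SAP counts every early withdrawal as event-free, so that the bias always favours the device. The documents do not support that. No denominator is assigned to the safety tables, and excluding event-free withdrawals would overstate the risk. Subjects who had a complication before leaving are counted, and a death on study is an event.

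A reader might also infer that the bias builds up to a large error at 60 months. SAP 2.3.2.3 and Appendix 4.1 item F present later events by interval (12-24 through 48-60 months), and no cumulative 60-month proportion is specified. What carries over is narrower: without numbers at risk, each later interval could be read against subjects who had already left.

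Finally, Kaplan-Meier is not a complete cure. If subjects leave because they are deteriorating, it is biased as well.

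**Conclusion.** The point holds as a gap in specification with a predictable direction on the only defined population. Used as the denominator, ITT yields a crude 12-month proportion below the true risk among treated subjects, through event-free withdrawal and through never-treated subjects.

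Under the assumed ranges, the shortfall from withdrawal is about 1% to 10% of the true risk in relative terms. The constant-hazard figures are roughly double those obtained when most of the hazard is peri-procedural, so the upper end should not be taken as typical. Informative withdrawal could change these figures.

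The unwritten choice of denominator matters more than either error alone. At 30% risk, 20% withdrawal and constant hazard, the same data read 27.1% or 32.6%, a gap of 5.5 points. The change is worth making because it is cheap and the absolute rate is the study's safety result. It does not put a formal test at risk, since none is planned.

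**What to change.** In SAP 1.2.2 and 2.3.2:
- Report the Kaplan-Meier cumulative incidence of first major complication in treated subjects, timed from treatment #1 and censored at last contact, with 95% confidence intervals at 30 days, 6 months and 12 months. Death is a component of the endpoint, so it raises no competing-event question.
- Give the number at risk for each time block, including the 12-24, 24-36, 36-48 and 48-60 month intervals. SAP 2.3.2.1 allows for subjects who miss Visit 5, so show the two peri-procedural windows separately.
- Keep the count table alongside, with its denominator stated.
- State one time origin. SAP 1.2.2 counts from baseline, whereas Appendix 4.1 item F counts from treatment #1.
- Show the reasons for premature termination next to the estimate, and say that it assumes non-informative withdrawal.

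The cost is SAP wording and one standard procedure. Appendix 4.1 already provides for onset dates and imputation of partial ones, and SAP 2.3.2.3 already lists onset in days relative to the procedure. The item to confirm is that a last-contact date is recorded for every subject. The downsides are that the reported rate may be slightly higher and that the estimate depends on the withdrawal assumption.
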